#### 43 Exclusion Criteria

- 1. Females who are pregnant, breast feeding, or planning a pregnancy during the course of the study and for 30 days after last study dose.
- 2. Females of childbearing potential who do not agree to utilize an adequate form of contraception.
- 3. Current or past history of severe hepatic or renal impairment, uncontrolled diabetes mellitus, rheumatoid arthritis or bleeding tendencies.
- 4. Current or history within two months prior to baseline of clinically significant ocular disease, e.g., corneal denervation, corneal epithelial defects, severe dry eye syndrome, ocular trauma to the operative eye, corneal edema, proliferative diabetic retinopathy in the operative eye or ocular infection.
- 5. In the operative eye, history of chronic or recurrent inflammatory disease, e.g., iritis, scleritis, uveitis, iridocyclitis or rubeosis iritis, lens pseudoexfoliation syndrome with glaucoma or zonular compromise.
- 6. Congenital ocular anomaly, e.g., aniridia or congenital cataract in the operative eye.
- 7. Iris atrophy in the operative eye in the operative eye.
- 8. Current corneal abnormalities that would prevent accurate IOP readings with the Goldmann applanation tonometer in the operative eye.
- 9. Nonfunctional nonoperative eye (visual acuity of 20/200 or worse Snellen).
- 10. Known hypersensitivity to any component of nepafenac therapy or to other nonsteroidal anti-inflammatory drug (NSAID).
- 11. Use within one week prior to baseline in either eye of: Topical, ophthalmic, e.g. cyclosporine (Restasis®), or systemic NSAID.

- 12. Use within one month prior to baseline in either eye of: 1) systemic corticosteroid, 2) high-dose salicylate therapy, or 3) topical ophthalmic prostaglandin analogs, e.g., bimatoprost, latanoprost, or travoprost.
- 13. Use of systemic analgesic medications, e.g. narcotics, tramadol, Neurontin® within 48 hours of baseline. Exceptions are salicylate therapy 81mg or less per day, and acetaminophen not within 8 hours of any visit from Visit 1 until V5.
- 14. Use within six months prior to baseline of intravitreal or subtenon injection of ophthalmic corticosteroid in either eye.
- 15. Underwent within six months prior to baseline any complicated intraocular surgery or repeat ocular surgeries (e.g., cataract surgery) in the operative eye.
- 16. Underwent within twelve months prior to baseline: refractive surgery, filtering surgery or laser surgery for IOP reduction in the operative eye.
- 17. History or presence of significant alcoholism or drug abuse in the past one year.
- 18. History or presence of significant smoking (more than 20 cigarettes or any other equivalent tobacco product/day). Discretion will be left to the Principal Investigator as to whether a patient with a history or presence of significant smoking will be included in the study.
- 19. History of hematologic disorders other than mild anemia.
- 20. Severe, unstable, or uncontrolled cardiovascular or pulmonary disease.
- 21. Therapy with an investigational agent within the past 30 days prior to screening.
- 22. Clinically significant hematologic and/or biochemical abnormalities based on laboratory testing.
- 23. Subjects who are in the investigator's best judgment at risk of visual field or visual acuity worsening as a consequence of participation in trial in either eye.
- 24. Use of any prescribed medication during last two weeks or OTC medicinal products during the last one week preceding the first dosing that results in drug-drug interaction with the study drug.
- 25. Major illness, as per investigator discretion, during 3 months before screening.
- 26. Subjects who are employees of site or CRO or sponsor or immediate family of employees.

#### 4.4 **Prohibitions:**

The following are prohibited during the study:

- a. Ophthalmic prostaglandin analogs, e.g., bimatoprost (Lumigan®), latanoprost (Xalatan®) or travoprost (Travatan®, Travatan Z®).
- b. Topical, ophthalmic, e.g. cyclosporine (Restasis®) and lifitegrast (Xiidra®), inhaled or systemic NSAIDs, other than the assigned study drug.
- c. Topical, ophthalmic, or systemic corticosteroid.
- d. Use of systemic analgesic medications, e.g. narcotics, tramadol, Neurontin®Intraocular corticosteroid implant.
- e. Intravitreal or subtenon injection of ophthalmic corticosteroid.
- f. High-dose salicylate therapy (>81mg/day).
- g. Medications which may prolong bleeding time (e.g. Warfarin®, Eliquis®) should be evaluated on a case-by-case basis by the investigator to determine if the subject is eligible to participate.
- h. Contact lenses in the operative eye. Contact lens use in the non-operative eye is acceptable.
- i. Ocular surgery in the study eye, other than study surgery.

#### 45 Allowable Co-Administrations:

The following are allowable drugs to be co-administered during the study:

- a. Coadministration of beta-blocker, carbonic anhydrase inhibitor, alpha-agonist, cycloplegic, mydriatic, and topical ophthalmic medications is permitted. When more than one topical ophthalmic medication is being used, the medicines must be administered at least 5 minutes apart.
- b. Coadministration of antibiotics, artificial tears, and low dose aspirin (less than or equal to 81 mg) is permitted.
- c. Subjects will be permitted to take acetaminophen as needed for ocular pain. Any use of acetaminophen will be recorded by the subject in the subject diary including Date (DD/MMM/YYYY), Dose (Mg), and Time (HH:MM).

Note: Adults and Adolescents Weighing 50kg or 110lbs and Over: 1,000mg every 6 hours or 650mg every 4 hours to a maximum of 4,000mg per day. Minimum dosing interval of 4 hours.

Adults and Adolescents Weighing under 50kg or 110lbs: the recommended dosage of acetaminophen injection is 15 mg/kg every 6 hours or 12.5 mg/kg every 4 hours, with a maximum single dose of acetaminophen injection of 15 mg/kg, a minimum dosing interval of 4 hours, and a maximum daily dose of acetaminophen of 75 mg/kg per day.

A minimum of 8 hours between the last dose of acetaminophen and assessment of ocular pain and aqueous cells and flare should be maintained.

# At least 5 minutes between all ophthalmic drop administrations should be maintained throughout the study.

#### 5.0 SAFETY AND TOLERABILITY EVALUATIONS

**5.1 General Safety Evaluations** 

#### **Adverse Events**

Safety will be determined by monitoring adverse events (AEs), which will be classified using MedDRA terminology.

#### **Medical History**

A complete medical history, including a complete review of all current and past diseases and their respective treatments, must be done prior to starting the study drug.

#### **Physical Examination**

Physical examination at the time of screening and on Day 14±2.

#### Vital Signs

Vital signs (blood pressure, pulse, respiratory rate and body temperature) at each study visit.

# Ophthalmic Evaluation (To be performed on both the operative and non-operative eye.)

Following examinations will be performed during study visits:

**Best Corrected Visual Acuity**: Subjects visual acuity will be measured during Visit 1, 4 & 5. Visual acuity will be tested using the subjects best-available spectacle correction with a Snellen chart. Best Corrected Visual Acuity will be recorded in Snellen units. Pinhole correction is acceptable method of correction to use for post-surgical visit measurements.

**Assessment of Ocular Pain:** When using the scale, the investigator should describe the meaning of pain to the subject. Then, verbally the subject should be asked to choose one of the six descriptors (provided in table no. 1 on page no. 13) that best represent the level of pain intensity a subject is experiencing.

**Slit Lamp Examination:** Complete slit-lamp evaluation including evaluation of the anterior eye segment for presence of aqueous cells and flare, lids, cornea, Anterior Chamber, iris and conjunctiva. Anterior Chamber evaluation is to be administered using a narrow slit beam (0.5 width at least 8 mm length) at maximum luminance. Pigment and red blood cells are to be ignored.

**Intraocular Pressure Measurement by Goldmann Applanation Tonometry:** Measurement of intraocular pressure will be recorded in millimeters of mercury (mmHg) by using Goldman applanation tonometry (manual version) during all visits except Visit 2 (On the day of cataract surgery).

**Dilated Fundus Examination:** A dilated fundus examination will be administered on the day of screening and at the end of the study visit (Visit 5 or early exit). In it, appropriate eye drops will be used to dilate or enlarge the pupil in order to obtain better view of the fundus of the eye. Once the pupil is dilated, an ophthalmoscope or indirect lens will be used to view the eye structures:

Lens	For opacities and other challenges	
Vitreous	Normal or Abnormal. Any changes, character	or location
CONFIDENTIAL Page 22 of 63		Page 22 of 63

Retina	Any pathological finding
Optic Nerve Head	Normal/ glaucomatous, horizontal and vertical cup/disc ratio

#### Laboratory Tests

The following laboratory tests will be performed at screening and at end of the study:

Serum Chemistry	ALT	AST	BUN
	Total Bilirubin	Glucose	Creatinine
Hematology	Hemoglobin	Total WBC count with differential	
Urinalysis	Appearance	Specific Gravity	Protein
	pH	Microscopic examination	

If warranted, other tests or examinations may be performed at the discretion of the investigator. Approximately 15 ml of blood will be withdrawn during screening visit and at the end of the study visit to perform above mentioned clinical laboratory test.

#### Pregnancy Test

Females of child bearing potential must have a negative urine pregnancy test performed during screening visit, at Visit 2, and at end of study or early termination visit (Visit 5).

All female study subjects are considered to be of childbearing potential unless they have been surgically sterilized or have been postmenopausal for at least 1 year.

Vital signs, including blood pressure, pulse rate, respiratory rate and body temperature will be documented at each visit.

Prior medication/Concomitant medications will be assessed at screening, baseline and at each subsequent study visit.

#### 6.0 EVALUATION OF EFFICACY

Proportion of subjects with cure at Visit 5 (End of study at day  $14 \pm 2$  days defined as a score of 0 for aqueous cells, a score of 0 for aqueous flare and a score of no more than 3 for pain.

#### 7.0 EVALUATION OF SAFETY:

- The incidence of treatment emergent adverse events.
- Ocular parameters (visual acuity, intraocular pressure measurement, slit lamp evaluation and dilated fundus examination).

#### 8.0 STUDY VISITS

#### 8.1 Visit 1: Screening/Baseline/Randomization Visit (Day-21 to day -1):

The following procedures will be performed at Visit 1:

1. Informed consent will be obtained from all participants who have confirmation on the

diagnosis of cataract and are planning to undergo cataract surgery. The latest version of IRB approved Informed Consent Form will be used for consenting process. The study subject will be allowed as much time as needed to read and understand the information presented in the informed consent form. Appropriate study personnel will be available to answer any questions the study subject might have regarding the study or study-related procedures. If the study subject chooses to participate in the study, he or she will be asked to sign and date the consent form and will be provided with a copy of the signed and dated consent form for his or her reference.

- 2. A complete medical history will be recorded. Information regarding the subject's current and past medical conditions will be captured including surgical procedures.
- 3. Review of prior medications which have been stopped/ongoing within 30 days prior to screening.
- 4. Demographics (Height, Weight, Age, Sex, Race/Ethnicity).
- 5. Physical Examination and Vital signs. At a minimum, the physical examination will include the following: assessment of general appearance, skin, HEENT, heart, lungs, musculoskeletal system, lymph nodes, neurological systems, gastrointestinal system, genitourinary system and extremities.
- 6. Assessment of ocular pain.
- 7. The study subject will be evaluated for iris color and complete slit lamp examination including a grading of the aqueous cells and aqueous flare.
- 8. Visual Acuity.
- 9. Intraocular pressure.
- 10. Fundus Examination.
- 11. A urine pregnancy test will be conducted for all females of childbearing potential.
- 12. The laboratory evaluation for routine hematology, biochemistry and urine analysis tests.
- 13. Assessment of any concomitant medications.
- 14. When the study subject has completed all screening procedures, the available data will be verified with the inclusion and exclusion criteria. Subject will be excluded from the study if any eligibility criterion is not satisfactory by the available information.
- 15. If eligibility criteria are satisfactory with the available information, the cataract surgery will be scheduled.
- 16. Randomize the patient in the study. CONFIDENTIAL

- 17. The patient should be instructed on how to administer the study medication, and be instructed to administer the study medication one day prior to the surgical day. To ensure that the study subject does administer the study medication one day prior to surgery the subject will be called the day before surgery and reminded to apply the study medication in the operative eye and bring both the subject diary and study drug on the day of surgery.
- 18. The study subject will be given a subject diary and instructed to document any medical events and any new medication used during the study.

#### Note: One Day Prior to Cataract Surgery (Day -1):

Subject should be called and reminded to administer study medication in operative eye and bring both the subject diary and study drug on the day of surgery. At least 5 minutes between all ophthalmic drop administrations should be maintained throughout the study.

#### 8.2 Visit 2: The Day of Cataract Surgery (Day 0):

- 1. Verification of study drug administration one day prior to surgery as required. Failure to comply with Day -1 study drug administration will result in the subject either proceeding with cataract surgery as scheduled but being withdrawn from the study, rescheduling of cataract surgery within 7 days of Screening/Baseline/Randomization Visit and proceeding on study, or cancellation of surgery and withdrawal from study.
- 2. Vital signs
- 3. Urine Pregnancy Test (for all females of childbearing potential)
- 4. Assessment of any concomitant medication
- 5. Assessment of Adverse Events
- 6. Administration of study drug to the operative eye should be administered 30-120 minutes prior to cataract surgery. (Administration of study drug should only be performed by the patient, caregiver, independent study drug administrator or unmasked personnel that are not assigned any other study duties). No masked members of staff should be involved in drug administration.

An additional drop of study drug should be administered post cataract surgery prior to the subject leaving the surgery center. (Administration of drug should only be performed by the patient, caregiver, independent study drug administrator or unmasked site personnel that are not assigned any other study duties). No masked members of staff should be involved in drug administration. The study is designed to be only monocular (only one eye per subject).

 Investigator should use the standard surgical methods, regimen of pre-operative and post-operative medication with the exception of NSAIDs and/or steroidal usage. CONFIDENTIAL Page 25 of 63

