#### **Study Duration:**

Total study duration will be of 16 days i.e. the treatment duration. A Screening period of up to 21 days is acceptable.

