## **APPENDIX I: SCHEDULE OF EVENTS**

Visit Details	Visit 1	Telephone Call	Visit 2	Visit 3	Visit 4	Visit 5
Study Activities	Day -21 to -1 Screening/ Baseline/ Randomization	Day -1 Pre-Operative Telephone Call	Day 0 The Day of Cataract Surgery	Day 1 One Day After Cataract Surgery	Day 7 + 2 days Follow-up visit	Day 14 + 2 days (End of Study / Early Discontinuation)
Informed Consent Process	×					
Medical History & Demographics	×					
Pre-Operative Call		×				
Physical Examination	×					×
Vital Signs	×		×	×	×	×
Inclusion/Exclusion Review	×					
Schedule the day for Cataract Surgery	×					
Assessment of Ocular Pain	×			×	×	×
Visual Acuity	×				×	×
Slit Lamp Examination	×			×	×	×
Intraocular Pressure	×			×	×	×
Fundus Examination	×					×
Laboratory Assessments (hematology, biochemistry and urine analysis)	×					×
Urine Pregnancy Test	×		×			×
Dispense/Administer Study drug	×		×	×	×	×
Dispense Subject Diary	×			×	×	
Retrieval/Review of Subject Diary					×	×
Retrieval of Study Medication						×
Concomitant Medication Assessment	×		×	×	×	×
Adverse Event Assessment	×	×	×	×	×	×

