3. STUDY OVERVIEW

3.1 Study Design

Approximately 450 subjects [REDACTED] will be enrolled and randomized in this investigational study. [REDACTED]

One drop of the suspension should be instilled into the affected eye one-time daily, beginning a day prior to the planned cataract surgery, on the day of the cataract surgery, and for 14 days thereafter. On the day of cataract surgery (day 0) a drop should be added 30-120 minutes prior to the surgery and an additional drop will be administered following cataract surgery prior to the subject leaving the surgery center. The study is designed to be only monocular (only one eye per subject).

The dose and mode of treatment chosen in this study is the dosage approved by US FDA for the treatment of pain and inflammation associated with cataract surgery.

The study subjects will undergo clinical evaluations throughout the study in order to assess efficacy and safety at the following visits:

- Visit 1: Day -21 to Day -1 (Screening/Baseline/Randomization Visit)
- Visit 2: Day 0 (The Day of Cataract Surgery)
- Visit 3: Day 1 (One Day After the Cataract Surgery)
- Visit 4: Day 7± 2 Days (Follow up Visit)
- Visit 5: Day 14 ±2 Days (End of Study Visit/Early Discontinuation)

An Unscheduled Visit is allowed at any time, for any reason, if in the Investigator's opinion it is warranted.

If the Investigator determines that the study subject's condition has worsened to the degree that it is unsafe for continuation in the study, the study subject may be discontinued and will be evaluated as a treatment failure.

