7.1.1 First Dose of the Study Drug

The dose of the study drug taken on the day prior to surgery will count as the first dose of the study drug.

It is possible that a subject is scheduled to have their surgery on a certain date, and according to the protocol, they take a drop of the study drug one day prior, however, then the surgery is rescheduled to a later date. In this case the subject would keep the IP, stop taking it, and apply a new drop before the new scheduled date of surgery. The very first drop taken prior to the date of cancelled surgery will count as the first dose of the study drug only for the purposes of determining the treatment-emergent status of AEs. It will not count as the first dose of the study drug for any other purposes, including, but not limited, to the following:

1. definition of baseline;
2. reference date for calculation of relative days;
3. calculation of study drug exposure and compliance.

Instead, the dose taken prior to the actual surgery will be considered as the first dose of the study drug.

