10. LITERATURE CITATIONS / REFERENCES

1. Study Protocol: "A randomized, multicenter, double masked, placebo controlled, parallel group, bioequivalence study to evaluate the clinical equivalence and safety of Nepafenac 0.3% ophthalmic suspension ([REDACTED] Actavis LLC) with Ilevro™ (Nepafenac ophthalmic suspension), 0.3% of Alcon Laboratories, Inc. for the treatment of pain and inflammation associated with cataract surgery", version 2.0 dated Feb 22, 2018.

11. APPENDICES**11.1 Study visit Schedule**

Visit Details	Visit 1	Telephone Call	Visit 2	Visit 3	Visit 4	Visit 5
Study Activities	Day -7 to -1 Screening/ Baseline/ Randomization	Day -1 Pre-Operative Telephone Call	Day 0 The Day of Cataract Surgery	Day 1 One Day After Cataract Surgery	Day 7 \pm 2 days Follow-up visit	Day 14 \pm 2 days (End of Study / Early Discontinuation)
Informed Consent Process	×					
Medical History & Demographics	×					
Pre-Operative Call		×				
Physical Examination	×					×
Vital Signs	×		×	×	×	×
Inclusion/Exclusion Review	×					
Schedule the day for Cataract Surgery	×					
Assessment of Ocular Pain	×			×	×	×
Visual Acuity	×				×	×
Slit Lamp Examination	×			×	×	×
Intraocular Pressure	×			×	×	×
Fundus Examination	×					×

Laboratory Assessments (hematology, biochemistry and urine analysis)	×					×
Urine Pregnancy Test	×		×			×
Dispense/Administer Study drug	×		×	×	×	×
Dispense Subject Diary	×			×	×	
Retrieval/Review of Subject Diary					×	×
Retrieval of Study Medication						×
Concomitant Medication Assessment	×		×	×	×	×
Adverse Event Assessment	×	×	×	×	×	×

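### After a missed Day -1 dose, the 7-day rescheduling limit in Protocol 8.2 cannot be met when surgery was booked 7 to 21 days after Visit 1

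*Protocol*

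**What the plan says.** Protocol 8.2 step 1 has the site verify at Visit 2, on the day of surgery, that the Day -1 drop was taken. If it was not, there are three outcomes:

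- surgery goes ahead as booked and the subject is withdrawn;
- "rescheduling of cataract surgery within 7 days of Screening/Baseline/Randomization Visit and proceeding on study";
- surgery is cancelled and the subject is withdrawn.

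The limit in the second outcome runs from Visit 1, not from the missed dose or the original surgery date.

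The Visit 1 window is 21 days wherever the protocol states it. The synopsis says "A Screening period of up to 21 days is acceptable", the title of section 8.1 reads "Screening/Baseline/Randomization Visit (Day-21 to day -1", and Appendix I shows "Day -21 to -1 Screening/ Baseline/ Randomization". SAP 3.1 agrees: "Visit 1: Day -21 to Day -1 (Screening/Baseline/Randomization Visit". Randomization is step 16 of Visit 1. The header of the visit schedule in SAP 11.1 differs and shows "Day -7 to -1 Screening/ Baseline/ Randomization".

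Two other provisions bear on the point. The note on Day -1 in Protocol 8.1 provides a reminder call: "Subject should be called and reminded to administer study medication in operative eye". SAP 7.1.1 covers a subject who took the drop and whose surgery was then moved: "the subject would keep the IP, stop taking it, and apply a new drop before the new scheduled date of surgery". It gives no limit in days.

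**The concern.** The limit in 8.2 suits a 7-day Visit 1 window, but the window is 21 days. For a subject whose surgery was booked a week or more after Visit 1, the limit is reached or already past when the missed dose is verified. The one outcome that would keep the subject on study is then unavailable, and the site must withdraw a randomized subject who has taken no study drug.

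The documents give no reason for the shorter limit. Screening data up to 21 days old are accepted for every other subject. A site that moved surgery beyond 7 days to keep the subject would depart from the protocol. Section 9.0 lists protocol violations as grounds for discontinuation, and SAP 6.3 ties per-protocol status to major deviations.

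What is at stake is sample size, mainly for the per-protocol equivalence comparison. The SAP 11.1 header adds a possible risk only: a programmed Visit 1 window check built from it would use the wrong window. The deviation definitions are in a separate document, so this cannot be confirmed.

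**Working it through.** **Day count**

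Inputs: Visit 1 falls on Day -k with k = 1 to 21 (Protocol 8.1); the miss is verified on Day 0 (8.2 step 1); a drop is required on the day before surgery (8.1 and 11.6); the limit is 7 days from Visit 1 (8.2 step 1).

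1. The booked surgery is k days after Visit 1, and the miss is verified on that day.
2. The make-up drop can be taken that day at the earliest, so the new surgery is at least k + 1 days after Visit 1.
3. The subject can stay on study only if k + 1 ≤ limit.

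| Limit from Visit 1 | Option open | Option closed |
|---|---|---|
| 7 days (current) | k = 1 to 6 (6 of 21) | k = 7 to 21 (15 of 21) |
| 21 days (proposed) | k = 1 to 20 (20 of 21) | k = 21 (1 of 21) |

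At k = 7 the earliest compliant new date is day 8. For k = 8 to 21 the limit has passed before the miss is verified. These are counts of permitted booking intervals, not shares of subjects.

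**Subjects affected (assumed rates)**

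The documents give neither the rate of missed Day -1 doses nor the distribution of k. Assume that 1% to 5% of 450 miss the dose and that 25% to 100% of those have k ≥ 7.

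- Missed doses: 450 × 0.01 = 4.5 to 450 × 0.05 = 22.5.
- Withdrawn, low end: 450 × 0.01 × 0.25 = 1.1.
- Withdrawn, high end: 450 × 0.05 × 1.00 = 22.5.

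That is about 1 to 23 subjects.

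**Effect on equivalence power (assumed design values)**

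Allocation and the sample size rationale are redacted, so there is no stated power to reproduce. Assume 150 per arm, 60% cure in both active arms, no true difference and no other loss from the per-protocol population. For the continuity-corrected 90% interval within ±0.20 (SAP 7.7.1.1), with n per arm:

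power = 2Φ[(0.20 − 1/n) / √(2 × 0.6 × 0.4 / n) − 1.645] − 1

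- n = 150: (0.20 − 0.00667) / 0.05657 = 3.418. Subtracting 1.645 gives 1.773, and power is **92.4%**.
- n = 150 − 22.5/3 = 142.5: (0.20 − 0.00702) / 0.05804 = 3.325. Subtracting 1.645 gives 1.680, and power is **90.7%**.

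The loss at the top of the range is 92.4 − 90.7 = 1.7 percentage points.

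**The case against.** The strongest objection is that this matters little. An affected subject has taken no drug and leaves at or before surgery, so would normally enter neither efficacy population. No test, margin or population definition changes. The reminder call comes on the day the drop is due, when it can still be taken. The top of the range needs a 5% miss rate despite that call and every such subject booked 7 or more days out. Power stays above 90% even then. The 1.7 points also credit the fix with keeping every such subject, although rescheduling is only one of three outcomes and depends on a free surgical slot. All of this stands. It limits the size of the point, but the limit in 8.2 still cannot be met for those booking intervals.

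A tighter limit after non-compliance might be deliberate. The documents do not settle this. That 7 days is left over from an earlier 7-day window, as the SAP 11.1 header suggests, is an inference. If the limit is intended, the protocol should give the reason and say that the option is not available for surgery booked 7 or more days after Visit 1.

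SAP 7.1.1 is weak support. It is an analysis convention for which drop counts as the first dose, it concerns subjects who did take the drop, and its silence on days sets no scheduling rule. The conclusion does not depend on it.

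**Conclusion.** The concern holds. As written, 8.2 step 1 forces withdrawal of any subject who misses the Day -1 drop and whose surgery was booked 7 to 21 days after Visit 1. This follows from the day count alone, and no other section relaxes the limit.

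The consequence is probably small and is not bias. The range of 1 to 23 subjects rests on assumed miss rates and booking intervals. The 1.7-point power loss also rests on assumed allocation and cure rates, and is an upper bound on what the change could recover within that scenario. The change is worth making because it is cheap and keeps randomized subjects who would otherwise be lost before any dose.

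**What to change.** In Protocol 8.2 step 1, change the limit from 7 to 21 days after Visit 1 and state that a drop is required on the day before the new surgery date. In the SAP 11.1 header, change the Visit 1 window to Day -21 to -1, so that any programmed window check uses 21 days.

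As a separate clerical item, align the protocol citation in SAP section 10 (version 2.0, February 22, 2018) with SAP section 1 (version 2.0, amendment 2.0, June 25, 2018). These may be a base version and its amendment; if so, section 10 should cite the amendment.

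The text changes are one phrase in the protocol, one SAP header and one SAP citation. The protocol change needs sponsor and IRB approval before use (Protocol 15.7) and must reach about 17 sites. It adds no visits, procedures or subjects, and screening data would be no older than the 21 days already accepted.
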